### 3.1 Main Treatment Period (Stages 1 and 2)

Stage 1 will include a screening visit; a maximum 8-week PN/I.V. optimization period (if required); and a stabilization period that demonstrates stable PN/I.V. support for a minimum of 4 weeks to a maximum of 8 weeks.

If at screening a subject does not have a stable PN/I.V. volume, defined as a 48-hour urine output within 2 to 4 L, he/she will enter the optimization period, during which the minimally tolerated stable PN/I.V. volume will be determined during a period of up to 8 weeks. If it is not possible to keep the subject adequately hydrated and nourished within the target urine output range, the minimally tolerated PN/I.V. volume will be documented.

All subjects will then enter the stabilization period, during which the target volume will be maintained for at least 4 consecutive weeks (8 weeks maximum) prior to entering the dosing period (Stage 2).

If a subject fails to maintain a stable PN/I.V. volume for at least 4 consecutive weeks, the subject may start the optimization period again, beginning with Week 2 (Visit 1.1). [Appendix 1](#) provides details of the optimization procedure. Those subjects who fail to stabilize after 2 attempts will not proceed further and will not be included in Stage 2.

Stage 2 will be a 24-week dosing period, during which subjects will self-administer teduglutide 0.05 mg/kg/day at home. Stage 2 will begin with baseline assessments of hydration and nutritional status once the subjects have demonstrated PN/I.V. stability for 4 to 8 weeks. At least

5 subjects will be enrolled. The on-treatment study visits will occur at Weeks 2, 4, 8, 12, 16 and 20, with the last scheduled visit at Week 24 of Stage 2.

[figure not shown]

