### 6.2.1.2 Procedures for Reporting Adverse Events

Adverse events may be spontaneously reported by the subject, obtained through nonleading questioning, or noted during examination of a subject. Adverse events will be recorded from the signing of the ICF and for the duration of the study. Adverse events that are not resolved at the end of study will be monitored with a telephone call by the investigator, as necessary, for approximately 4 weeks after the last dose of study drug or until resolution or until the AE is judged by the investigator to have stabilized.

As they occur, new AEs will be recorded sequentially on the AE page of the CRF. The AE term should note the diagnosis whenever possible, not the individual signs or symptoms (eg, myocardial infarction should be recorded rather than chest pain, elevated cardiac enzymes, and abnormal ECG). Also recorded are:

- Start and stop date and time (date the site becomes aware of the SAE)
- Whether the event is continuing
- Frequency (intermittent, continuous)
- Intensity (mild, moderate, severe)

- Mild: usually transient, requiring no special treatment and generally not interfering with usual daily activities
- Moderate: usually ameliorated by simple therapeutic maneuvers and impairs usual activities
- Severe: requires vigorous therapeutic intervention and interrupts usual activities. Hospitalization may or may not be required
- Relationship to study drug (not related, related): identify relationship as “related” if a causal relationship between the investigational product and an AE is at least a reasonable possibility (see Section [6.2.2.2](#) for additional guidance on relationship to study drug)
- Whether the AE is serious (ie, an SAE). If identified as an SAE, the AE should be reported on the SAE form according to Section [6.2.2](#) below.
- Actions taken (none; study drug dose changed, interrupted, or discontinued; other medication change; nondrug therapy)
- Outcome (not recovered/not resolved, recovered/resolved, recovered/resolved with sequelae, recovering/resolving, unknown, fatal). An individual AE receives only one outcome.

Laboratory values, blood pressure, ECG evaluations, and clinical findings at the scheduled physical examinations must be reported as AEs if they:

- Are considered clinically significant by the investigator (ie, not part of the subject’s medical history),
- Fulfill SAE criteria, and/or
- Cause subject discontinuation from the study.

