## 6.2.2 Serious Adverse Events

An SAE must be recorded on the SAE Form. An SAE requires expeditious handling to comply with regulatory requirements. Any SAEs occurring from the signing of the ICF through 30 days after the last dose of study drug or the end of the study, whichever is longer, will be captured and must be reported within 24 hours after the investigator is made aware of the event.

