### 6.2.2.2 Procedures for Reporting Serious Adverse Events

All initial and follow-up SAE reports must be reported by the investigator to the sponsor's Global Drug Safety Department and the CRO/Shire Medical Monitor within 24 hours of the first awareness of the event. Note: The 24-hour reporting requirement for SAEs does not apply to reports of abuse, misuse, overdose, or medication errors (see Section 6.2.1.1) unless they result in an SAE.

The investigator must complete, sign, and date the sponsor's Clinical Study Serious Adverse Event and Non-serious AEs Required by the Protocol Form and verify the accuracy of the information recorded on the form with the corresponding source documents (Note: Source documents are not to be sent unless requested) and e-mail the form to the sponsor's Global Drug Safety Department. A copy of the sponsor's Clinical Study Serious Adverse Event and Non-serious AEs Required by the Protocol Form (and any applicable follow-up reports) must also be sent to the sponsor's Medical Monitor using the details specified in the emergency contact information section of the protocol.

Note: Minimum criteria for reporting an SAE are the SAE term, an identifiable subject, a suspect investigational medical product (study drug), and a reporter. Hospitalization is not an AE, but an SAE criterion. The SAE term is the medical event that led to the hospitalization. Surgery is not an AE, but the event that required the subject to have surgery is the SAE term. Death is not an SAE, but an outcome.

Autopsy reports, if applicable, will be forwarded as they become available. All pertinent laboratory results should be entered on the SAE form.

All SAEs must be reported, whether or not they are considered causally related to the study drug. Appropriate clinical, diagnostic, and laboratory measures should be performed to delineate the

cause of the SAE in question and the results reported. Follow-up for the SAE should occur at appropriate intervals until the event/laboratory abnormality:

- Returns to baseline or
- Becomes stable to a clinically acceptable level that is safe for the subject.

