### 8.3.1 Statistical Methods for Safety Variables

Adverse events will be coded using the most recent version of the MedDRA dictionary. Treatment-emergent AEs will be summarized by system organ class and preferred term using descriptive statistics (eg, number and percentage of subjects). Adverse events will be summarized by severity, relationship to treatment, AEs leading to discontinuation, and AEs leading to death. SAEs will also be tabulated by overall and treatment-related events.

For laboratory tests, 48-hour urine output, vital signs, body weight, BMI, and ECG variables, descriptive statistics (eg, n, mean, standard deviation, median, minimum and maximum values, the number and percentage of subjects in specified categories) will be used to summarize the absolute values and change from Baseline at each time point.

The number and percentage of subjects classified as having antibodies to teduglutide will be used to summarize the presence of antibodies.

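### Section 6.2.1.2 ties the adverse event start and stop dates to the date the site learned of the SAE, merging onset with awareness, which Sections 6.2.2 and 6.2.2.2 keep apart

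*Protocol*

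**What the plan says.** All references are to the current, four-stage version of the protocol.

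Section 6.2.1.2 applies to every adverse event, serious or not: "As they occur, new AEs will be recorded sequentially on the AE page of the CRF". A list of the items to record follows. The first item, and the only one that gives dates, is "Start and stop date and time (date the site becomes aware of the SAE", closing with a bracket. The same wording stands in the two three-stage versions in the same document, so it has been carried forward.

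Section 6.2.2 defines SAE capture by occurrence, from signature of the consent form "through 30 days after the last dose of study drug or the end of the study, whichever is longer". The same sentence sets the reporting duty by awareness: each SAE "must be reported within 24 hours after the investigator is made aware of the event". Section 6.2.2.2 repeats the clock: reports are due "within 24 hours of the first awareness of the event".

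Two uses of the data need the date on which the event began. Section 8.3.1 states that "Treatment-emergent AEs will be summarized by system organ class and preferred term". The causality guidance in Section 6.2.2.2 rests a judgement of related or not related partly on the timing of the event relative to administration of the product.

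**The concern.** A bracket placed after a data item normally explains that item. Here it names a different quantity. Onset decides whether an event is treatment-emergent and whether it falls in the SAE capture window. Awareness decides only whether the site reported in time. A site that follows the bracket for an SAE would enter the awareness date where the analysis expects onset.

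The protocol and the form fix what is collected. An analysis plan can define treatment-emergence, but it has to work with the dates it receives. If the onset of an SAE was never entered, no later rule restores it.

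**Working it through.** No stated figure is in question, so the check sets the passages side by side.

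**Which date each rule uses**

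- Section 6.2.1.2, list for all adverse events: start and stop, glossed as SAE awareness.
- Section 6.2.2, SAE capture: the date the event occurs.
- Sections 6.2.2 and 6.2.2.2, 24-hour clock: the date of awareness.
- Section 8.3.1, treatment-emergent summaries: onset relative to first dose.
- Section 6.2.2.2, causality: timing of the event relative to dosing.

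Only the first of these merges the two dates.

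**Literal reading for an SAE.** Let O be onset, A the awareness date and D the first dose. The recorded start becomes A instead of O, an error of A − O, which is zero or positive. The shift therefore runs one way. An SAE is misclassified when O falls before D and A falls after it, and it then enters the treatment-emergent tables. An event that began on treatment cannot be moved to before first dose. Events before dosing are within scope, because recording starts at consent and the protocol summary gives Stage 1 a possible length of 1 + 16 + 16 = 33 weeks.

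**Literal reading for a non-serious event.** The bracket mentions only the SAE, while the list covers all events. It gives no instruction that can be applied to a non-serious event, so the text is unclear but substitutes nothing.

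**Coherence.** A single awareness date cannot be both a start and a stop. The item is therefore faulty as worded, whatever was meant.

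**Size of the lag.** Section 3.1 states: "The on-treatment study visits will occur at Weeks 2, 4, 8, 12, 16 and 20", with the last Stage 2 visit at Week 24. From Week 4 the spacing is 4 weeks. If an SAE were learned of only at the next planned visit, A − O could reach 4 × 7 = 28 days in Stage 2. This is an upper bound between planned visits, ignoring visit windows and unscheduled contact. It bears on causality timing. For misclassification at first dose, any lag that spans Day 0 is enough.

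**Size in the tables.** One reclassified subject changes an incidence by at most 1/n. Section 4.1 plans at least 5 subjects, so the upper bound is 1/5 = 20 percentage points, and it falls as n grows. It is reached only if that subject has no other event counted in the same row.

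**The case against.** The strongest reply is that this is a misplaced bracket and nothing more. The item itself asks for start and stop dates, and the next one asks whether the event is continuing, which presumes a real stop date. The natural reading is that an extra SAE field, the awareness date, was put in the wrong place. Nothing in Sections 6.2.2, 6.2.2.2 or 8.3.1 suggests an intention to date events by awareness. Sites also receive CRF guidelines (Section 7.1), which may have a proper onset field. All of this stands. It makes the defect one of wording, with misdating possible but not shown.

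Misclassification at first dose is also unlikely to be common. In the earlier version of Table 6-2, where the row is legible, adverse events are asked about at the baseline visit on Day 0. An SAE from Stage 1 would have to be missed at that enquiry and surface later.

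Some stronger readings are tempting but not supported:

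- A reader might infer that the protocol nowhere asks for onset. The item does ask for it, and the bracket then confuses it.
- A reader might infer that SAEs fall out of the 30-day window. Section 6.2.2 already goes by occurrence and extends the window to the end of the study if that is longer. Comparing the three-month spacing of Stage 4 visits with the 30 days also measures nothing, since those visits are on treatment and inside the window on either date.
- A reader might infer wrong results by stage, for duration or for time to onset. Section 8.3.1 plans none of these summaries and does not call any safety table primary.

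What the reply does not remove is the inconsistency in a rule that sites are told to follow. The reading that rescues the item has to be supplied by the reader.

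**Conclusion.** The point holds as a small but real inconsistency in a data-collection rule. For SAEs, the literal reading replaces onset with awareness. That could count a late-learned pre-dose SAE as treatment-emergent and weaken the timing on which causality is judged. For non-serious events the wording is ambiguous only.

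The effect on any one incidence is at most 20 percentage points at the minimum of 5 subjects. The documents give no basis for saying how often it would happen.

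The conclusion rests on two assumptions: that a site follows the bracket as written, and that the case report form and its guidelines do not correct it. Neither can be checked from the protocol. The point is worth acting on because the correction is trivial, while a wrong onset date may not be recoverable after collection.

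**What to change.** Split the item in Section 6.2.1.2 in two:

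- for every adverse event, *start and stop date and time of the event*;
- for SAEs only, *date the site became aware of the event*.

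Add one sentence: onset governs treatment-emergence and the occurrence-based SAE capture window, and the awareness date governs only the 24-hour reporting clock. Check that the case report form and the CRF guidelines have both fields. If SAEs have already been entered, ask sites to confirm that the recorded start is the onset.

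The cost is one line in the protocol and a matching line in the guidelines. No visit, procedure, dose or analysis changes.

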### 6.2.1.1 Adverse Event Definition

An AE is defined as any untoward medical occurrence in a subject or clinical investigation subject administered a pharmaceutical/medicinal product. An AE does not necessarily have to have a causal relationship with this treatment.

An AE can therefore be any unfavorable and unintended sign (including a clinically significant abnormal laboratory finding, for example), symptom, or disease temporally associated with the use of a medicinal product (investigational or marketed), whether or not considered related to treatment with the medicinal product.

An AE includes:

- An exacerbation of a pre-existing illness, sign, symptom, or clinically significant (as determined by the investigator) laboratory test abnormality and clinically significant ECG abnormality
- An illness, sign, symptom, or clinically significant laboratory abnormality that is detected or diagnosed after study drug administration
- Pretreatment or post-treatment events that occur as a result of protocol-mandated procedures

An AE does not include:

- The disease or disorder being studied or signs and symptoms associated with the disease or disorder, unless there is worsening of the condition of the disease or disorder
- A pre-existing disease or condition, present at the start of the study, that does not worsen

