### 6.2.5 Laboratory Evaluations

Laboratory results can vary depending on whether samples are drawn on an on- or off-PN/I.V. day, so it is important that every effort be made to draw laboratory samples on the same type of infusion day (ie, on- or off-PN/I.V.) throughout the study. Although subjects do not need to be in a fasted state at the time of their clinic visit, they should avoid large meals or large volumes of fluid, including PN/I.V. with lipids, within 3 hours of the clinic visit to permit consistent assessment. If peripheral venous access is not possible, the sample may be drawn from the central line. A home nursing visit may be appropriate to collect samples in some circumstances. The site's clinical laboratory will centrifuge and send the samples to the central lab, SRL Medisearch Inc. to be analyzed. Citrulline, antibody, and PK samples will be handled according to procedures specified in the laboratory manual.

Clinically significant (as determined by the investigator) abnormal laboratory test results will be considered AEs if they are not related to the subject's underlying condition or their previous comorbid medical history (unless they are a worsening of the condition). A result outside of the normal range may be repeated for confirmation. Any laboratory test result that meets the criteria for an SAE (Section 6.2.2) must also be recorded in an SAE Form so that the sponsor or designee can collect additional information about that abnormality, including information regarding relationship to investigational product or other causes, any action taken, and outcome.

The following laboratory parameters will be collected according to the Schedule of Evaluations and Procedures outlined in [Table 6-1](#), [Table 6-2](#), [Table 6-3](#), and [Table 6-4](#):

- Hematology

Hemoglobin, hematocrit, erythrocyte count, platelet count, and leukocyte count with differential

- Serum chemistry

Albumin; alkaline phosphatase; ALT; amylase; AST; total, direct, and indirect bilirubin; blood urea nitrogen; calcium; chloride; total-cholesterol; C-reactive protein; creatinine; creatinine clearance; gamma glutamyl transferase; glucose; lipase; magnesium; phosphate; potassium; sodium; triglycerides; and uric acid

- Urinalysis

Blood, glucose, leucocytes, microscopic, pH and osmolality, protein, and sodium

- Pregnancy test

Urine pregnancy test (women of childbearing potential [WOCBP] only)

- Antibodies to teduglutide and ECP

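### Section 6.2.1.2 leaves worsening of a known abnormality out of its adverse-event reporting rule, against 6.2.1.1, 6.2.5 and (for blood pressure) 6.2.15

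*Protocol*

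**What the plan says.** Section numbers are those of the current, four-stage version of the Protocol.

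- **6.2.1.1 (definition).** An AE includes "An exacerbation of a pre-existing illness, sign, symptom, or clinically significant (as determined by the investigator) laboratory test abnormality" and also "An illness, sign, symptom, or clinically significant laboratory abnormality that is detected or diagnosed after study drug administration". The list of what is not an AE contains "A pre-existing disease or condition, present at the start of the study, that does not worsen". Signs of the studied disease are likewise left out only while they do not worsen.
- **6.2.1.2 (reporting procedure).** Laboratory values, blood pressure, ECG evaluations and "clinical findings at the scheduled physical examinations must be reported as AEs if they" meet any of three criteria. The first is that they "Are considered clinically significant by the investigator (ie, not part of the subject’s medical history"). The second is "Fulfill SAE criteria, and/or" and the third is "Cause subject discontinuation from the study".
- **6.2.5 (laboratory).** Clinically significant abnormal results "will be considered AEs if they are not related to the subject's underlying condition or their previous comorbid medical history". A parenthesis then restores those that are a worsening of the condition.
- **6.2.15 (vital signs).** Changes that the investigator judges clinically significant go on the AE page. Medical history is not mentioned.

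**The concern.** The parenthesis in 6.2.1.2 opens with *ie*, so it reads as an explanation of what clinically significant means: absent from the medical history. A finding already in the history then fails the first criterion even if it has become much worse. The definition in 6.2.1.1 says the opposite.

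Section 6.2.1.2 is the procedure that governs entries on the AE page, and the TEAE summaries in 8.3.1 (by system organ class, severity, relationship and discontinuation) are built from those entries. If some sites follow the definition and others the procedure, the same event is counted at one site and not at another. The trial has no control arm, so there is no parallel group in which the same undercount could be seen.

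The situation is plausible in this population. Exclusions 17 and 18 in 4.3 admit AST and ALT below 5 times ULN, and total bilirubin and serum creatinine below 2 times ULN. Subjects can therefore enter with values that are already abnormal.

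**Working it through.** The plan gives no figure on this point, so the check is a comparison of rules on one test case: a clinically significant worsening of an abnormality that is in the medical history, not serious, and not leading to discontinuation.

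| Section | Findings covered | Treatment of worsening | Test case |
|---|---|---|---|
| 6.2.1.1 | All | Exacerbation is included; a pre-existing condition is left out only if it does not worsen | AE |
| 6.2.5 | Laboratory | History-related results are left out, but worsening is restored | AE |
| 6.2.15 | Vital signs, including blood pressure | No history condition | Goes on the AE page |
| 6.2.1.2 | Laboratory, blood pressure, ECG, examination | Criterion 1 leaves out what is in the history, with no worsening clause; criteria 2 and 3 are not met | Meets none of the three |

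Varying the test case shows how wide the gap is:

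- Serious worsening meets criterion 2 of 6.2.1.2.
- Worsening that leads to discontinuation meets criterion 3.
- A clinically significant finding not in the history meets criterion 1.

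The sections therefore part only on non-serious worsening of a known abnormality in a subject who stays in the study.

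The next question is what the planned summaries still show if such an event is left off the AE page:

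- **Laboratory values and 48-hour urine output.** 8.3.1 summarizes values and change from baseline at each time point, whatever their AE status. The data stay visible, and 6.2.5 states the right rule for laboratory results.
- **Blood pressure.** It is summarized the same way, and 6.2.15 sends significant changes to the AE page.
- **ECG.** 8.3.1 lists ECG variables, but 6.2.16 captures results only as normal or abnormal. A subject who is abnormal at baseline and gets worse is still abnormal, so no change shows.
- **Physical examination.** It is not in the list of variables summarized in 8.3.1. The AE page is the main route into the planned summaries.

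On size, 4.1 plans at least 5 subjects. At exactly 5, one subject left out of an incidence moves it by 1/5 = 20 percentage points. This holds for any single subject at that number and shrinks as enrolment rises. It describes how coarse the table is and does not estimate the undercount.

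**The case against.** The strongest reply is that 6.2.1.2 does not override the definition. It says that findings must be reported if they meet a criterion, not only if they do. The same section also tells sites to record new AEs on the AE page as they occur, and what counts as an AE is fixed in 6.2.1.1. On that reading the worsening is recordable anyway. This is right as a reading of the Protocol as a whole, and it limits the point to inconsistent application by sites. It does not remove the problem, because the *ie* gives sites a meaning of clinically significant that contradicts the definition.

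A reader might also infer four stronger claims that the documents do not support:

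- **That three sections set three conflicting tests.** On worsening, 6.2.1.1 and 6.2.5 agree; 6.2.1.2 is the outlier.
- **That 6.2.1.2 drops every finding in the medical history.** Its SAE and discontinuation criteria carry no history condition.
- **That worsening liver, renal or hydration values are lost.** For laboratory results 6.2.5 is the specific rule and keeps worsening as an AE, and 8.3.1 summarizes the values regardless. The entry limits are laboratory thresholds at stabilization and do not show that anything was recorded as medical history.
- **That TEAE incidences will be 20 points too low.** No rate of misapplication is given or derivable, and 5 is a floor.

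**Conclusion.** The point holds in a narrow form. The parenthesis in 6.2.1.2 contradicts 6.2.1.1 and 6.2.5 on worsening, and for blood pressure also 6.2.15. If sites follow it literally, non-serious worsening of known abnormalities is undercounted among TEAEs, and the count varies with the section a site uses. The effect is mainly on TEAE counts, and is greatest for examination findings and ECGs, where the planned summaries offer little or no fallback. Its size cannot be stated.

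The conclusion assumes that some sites would work from 6.2.1.2 as a checklist and read the parenthesis as written. The Protocol neither confirms nor rules this out. The correction is worth making because the conflict lies in one phrase and can be removed at almost no cost.

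**What to change.** In the first criterion of 6.2.1.2, extend the parenthesis so that the reference to medical history is followed by *or a worsening of it*. The criterion then matches 6.2.1.1 and 6.2.5 for all four kinds of finding, and no longer conflicts with 6.2.15 for blood pressure.

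Leave 6.2.5 unchanged. Its restriction already has the worsening exception and follows the same logic as the definition, so deleting it would go beyond what the conflict requires.

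The cost is one phrase in an amendment and possibly a few more AE records. No new assessments are needed and clinical management is unaffected.
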